# **Document History**

Version	Date	Description
V0.1	09/01/2018	First draft
V0.2	22/01/2018	Comments
V0.3	13/03/2018	Comments, 2nd round
V0.9	27/04/2018	Semifinal version
V1.0	04/06/2018	Version approved by Independent Scientific Committee
V1.1	05/12/2018	Updated codebook / minimum dataset requirement

## List of abbreviations

DRIVE	Development of Robust and Innovative Vaccine Effectiveness
ECDC	European Centre for Disease Prevention and Control
EEA	European Economic Area
ENCePP	European Network of Centres for Pharmacoepidemiology & Pharmacovigilance
EU	European Union
GEP	Good Epidemiological Practice
GP	General Practitioner
ICD	International Classification of Diseases
IMI	Innovative Medicines Initiative
ILI	Influenza-like illness
IVE	Influenza vaccine effectiveness
MAH	Marketing Authorization Holder
OR	Odds ratio
RT-PCR	Real Time Polymerase Chain Reaction
SARI	Severe Acute Respiratory Infection
TND	Test-negative design
VC	Vaccination coverage
VE	Vaccine effectiveness
WHO	World Health Organization

# Preface

The IMI project DRIVE aims to create a European platform for studying brand-specific influenza vaccine effectiveness (IVE) and to develop a governance model for scientifically robust, independent and transparent implementation of IVE studies in a public-private partnership.

In DRIVE, data from several independently operating national or regional study sites will be analysed jointly to obtain sufficient geographical coverage and sample size for brand-specific IVE estimates. DRIVE recognizes the value of current study networks and strives to include secondary data from existing studies and initiatives. This is expected to foster European cooperation and maximize the sustainability of the pooled IVE studies.

The main objective of the 2017/18 pilot season is to test the different operational aspects of the DRIVE project, including governance, data collection, statistical analyses and dissemination of study results. Consequently, the number of study sites for this season is limited with narrow possibility to study the full range of vaccine brands used across Europe.

This generic protocol is intended to be adapted to the local procedures at each individual study site from season 2018/19 onwards. Its aim is to achieve maximum harmonization between the different sites while respecting their different backgrounds. Experience from the pilot studies, together with the completion of other, interconnected DRIVE tasks, will inform the subsequent versions of the protocol.

# Background

Influenza is a major public health burden. It is responsible for an estimated 50 million disease episodes and 15,000 to 70,000 deaths in the European Union (EU) and European Economic Area (EEA) Member States each year, although with considerable variation from season to season [2] and by methodology used [3]. Complications including deaths are more common in the elderly and in children younger than one year of age [4]. Vaccination is considered as the most effective means for preventing influenza and its complications [5] and the World Health Organization (WHO) has set a vaccination coverage target of at least 75% in the elderly population and among risk groups [6].

Due to frequent genetic and antigenic changes in influenza viruses, the seasonal vaccine is regularly reformulated (almost annually) to match with the characteristics of the viruses circulating and annual vaccination is recommended.

Observed IVE varies year-to-year due to a variety of reasons including mismatch between the vaccine virus strains and the circulating strains, waning immunity and possible interference from previous vaccinations [6, 7]. In the last two decades, controversies have sprung around the effectiveness of influenza vaccines [8]. While past IVE estimation efforts have led to significant achievements using generic protocols, standard methodologies and laboratory confirmation, several questions about IVE remain open.

In its new guideline on influenza vaccines, the European Medicines Agency (EMA) [9] requires that observational IVE studies be conducted in the EU/EEA as part of the post-licensure requirements of the vaccine manufacturers. Specifically, manufacturers are requested to replace the annual clinical immunogenicity trials (with no clear correlates of protection) with vaccine effectiveness data, that will provide product specific data. To reach this goal, manufacturers are encouraged to liaise with organisations/institutions/public health authorities. The studies are expected to be conducted in line with Good Epidemiological Practice (GEP) guidelines and with European Network of Centres for Pharmacoepidemiology & Pharmacovigilance (ENCePP) guidelines.

This document presents the generic DRIVE protocol for the field-based test-negative design (TND) study with patients seeking care for influenza-like illness (ILI) or severe acute respiratory infections (SARI). While each of the study sites can be analysed separately, pooling them into one analysis is expected to provide a sample size large enough to answer more specific study questions (such as type and age specific VE estimates) with a reasonable/greater precision. The protocol builds upon the European Centre for Disease Prevention and Control (ECDC) Protocol for case-control studies to measure pandemic and seasonal influenza vaccine effectiveness in the European Union and European Economic Area Member States [10] and the WHO guide to the design and interpretation of observational studies [11]. It will be updated according to the pilot conducted in the participating EU member states, starting from the 2018/2019 season. The details of each site-specific study will be provided in the study annexes (e.g. ethical committee clearance, study form used, data collection strategy, etc.).

# **Objectives**

## **Primary objective**

To measure seasonal IVE against medically attended (primary care/hospital) laboratory-confirmed influenza, by vaccine brand, then by vaccine type (e.g. by antigen preparation strategy, number of virus strains, adjuvant; see section Exposure), then by overall influenza vaccination.

## Secondary objectives

To estimate IVE (brand-specific, type specific and total, if possible) against laboratory-confirmed influenza by:

- age group (6 months-14 years; 15-64 years; 65+ years, the age groups will be further defined when harmonising the study protocols between study sites according to availability of data)
- influenza virus type (A, B) and/or subtype (A/H1N1, A/H3N2) and lineage (B/Victoria, B/Yamagata)
  - o risk groups / target groups for vaccination,
  - o pregnant women
  - o healthcare workers
  - any chronic condition (see annex 1)
  - specific chronic conditions (see annex 1)
- time since vaccination
- time window in the epidemic season (early, middle, end) (see study period section)
- previous influenza vaccinations (at least one previous season, preferably more)

To estimate IVE across:

• several seasons

The details of the analyses will be prescribed in the generic and study site specific SAP, updated annually according to the characteristics and structure of data available at the participating study sites.

# **Methods**

#### Study design

> A multicentre study using data from several study sites

In each participating study site, an observational case-control study using the test-negative design

## Study setting

The studies may take place in a primary care or a hospital setting. The study setting is defined by each study site depending on the available data.

- Each study site to specify if the study is nested into the influenza surveillance scheme (the ILI sentinel surveillance system) or is organized differently
- Each study site to specify national policy for influenza surveillance and vaccination and available vaccine brands on the market
- > Each study site to specify the target groups for which influenza vaccination is recommended

## **Study period**

The seasonal assessment will start when the influenza virus circulation begins (first virus detected at the national/study site level) in the country/region and will finish at the end of the influenza season (no cases detected during 2 consecutive weeks or equivalent).

Each study site to specify the assessment period: the definition of the beginning, peak and end of the influenza period at the study site according to the information provided by the local influenza surveillance system (including information on the type of virus circulating and virulence of the virus)

For the joint analysis, a harmonised minimum period will be defined (e.g. from week 40 till week 20), but if needed, it will be extended to fully cover the vaccination campaign and the epidemic in each study site. Definition of shorter time periods (e.g. early, middle and end season) will be developed to take into account differences in influenza activity over time and probable development of immunity in unvaccinated population through encounters with the circulating viruses

For addressing the secondary objective of estimating influenza vaccine effectiveness over several seasons, multiple study periods will be combined.

## **Study population**

The study population consists of patients seeking care (i.e. subjects consulting their GPs, or an emergency department/hospital) for symptoms compatible with ILI or SARI aged 6 months and above, with no contraindication for influenza vaccination.

Each study site to specify the study population and the case finding procedure, please see the Case finding section.

## Outcomes

The outcome of interest is laboratory-confirmed influenza in the study population. More specifically:

- subtype-specific laboratory-confirmed influenza A,
- laboratory-confirmed influenza B overall and if available by lineage (B Victoria/B Yamagata),

• laboratory-confirmed influenza by clade (where possible).

### **Case definition**

#### Influenza-like illness (ILI)

A case of influenza like illness (ILI) will be defined by the ECDC case definition as an individual who presents with a sudden onset of symptoms including at least one of the following four systemic symptoms:

- fever or feverishness;
- malaise;
- headache;
- myalgia;

#### AND

at least one of the following three respiratory symptoms:

- cough;
- sore throat; and
- shortness of breath.

#### Severe acute respiratory infection (SARI)

A case of severe acute respiratory infection (SARI) will be defined by the SARI - IMOVE+ 2017/2018 case definition as a hospitalised person with

 at least one systemic symptom or sign (fever or feverishness, malaise, headache or myalgia), or deterioration of general condition (asthenia or loss of weight or anorexia or confusion or dizziness)

#### AND

• at least one respiratory symptom or sign (cough, sore throat or shortness of breath)

at admission or within 48 hours after admission. The symptoms should not have started (or, if chronic, clearly worsened) more than 7 days before swabbing.

#### Primary care studies

- Case: ILI laboratory-confirmed influenza. An ILI patient will be defined as a person in the study population, meeting the ILI EU case definition with a respiratory sample positive for influenza (see Laboratory testing section).
- Control: ILI negative for Influenza. A control will be defined an ILI patient in the study population, meeting the ILI - EU case definition for clinical criteria, with a respiratory sample negative for influenza.

#### Hospital studies

• Case: SARI confirmed as Influenza. A SARI patient will be defined as a person in the study population, meeting the clinical case definition with a respiratory sample positive for influenza (see laboratory testing section).

• Control: SARI negative for Influenza. A control will be defined as a SARI patient in the study population, meeting the clinical case definition with a respiratory sample negative for influenza.

## **Case finding**

#### ILI and SARI patient identification

Patients will be identified among people who present at a healthcare provider (GPs or Hospitals) with influenza-like illness (ILI) or severe respiratory acute infection (SARI).

- > Each study site to provide exclusion criteria applied, if different from the list described below
- > Each study site to describe procedures to identify study participants

#### Inclusion criteria

ILI/SARI patients are eligible if they accept to participate and do not fulfill any of the exclusion criteria.

#### **Exclusion criteria**

The ILI patient will not be enrolled in the study if she or he:

- Is less than 6 months of age at the time of recruitment
- has a contraindication for influenza vaccine
- is unwilling to participate or unable to communicate and give consent (the consent may also be given by her/his legal representative, or by specific consent procedures, acceptable according to the local ethical review process)
- is institutionalised at the time of symptoms onset (lives in a residence for people who require continual nursing care and have difficulty with the required activities of daily living)
- had a respiratory specimen taken ≥ 8 days after ILI onset
- tested positive for any influenza virus in the current season before the onset of symptoms leading to the current primary care visit/hospitalisation

The SARI patient will not be enrolled in the study if she or he:

- Is less than 6 months of age at the time of recruitment
- has a contraindication for influenza vaccine
- was previously hospitalised < 48 hours prior to ILI onset
- had his/her ILI onset ≥ 48 hours after admission at the hospital
- is unwilling to participate or unable to communicate and give consent (the consent may also be given by her/his legal representative, or by specific consent procedures, acceptable according to the local ethical review process)
- is institutionalised at the time of symptoms onset (lives in a residence for people who require continual nursing care and have difficulty with the required activities of daily living)

- had a respiratory specimen taken ≥ 8 days after ILI onset
- tested positive for any influenza virus in the current season before the onset of symptoms leading to the current hospitalisation

Note: a patient can be selected several times as long as he/she does not have a previous laboratory confirmed influenza for the current season

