#### Definition of vaccination status

An individual aged  $\geq$ 9 years, or a child aged <9 who has been fully vaccinated (at least two injectable doses or one LAIV dose) during the previous influenza season will be considered as

- vaccinated with the influenza vaccine of interest if he/she has a record of influenza vaccine administration >14 days before ILI/SARI symptom onset (see section Vaccination status ascertainment)
- partially vaccinated if he/she has a record of influenza vaccine administration ≤14 days

before ILI/SARI symptom onset

- **unvaccinated** if he/she has no influenza vaccine record for the current season
- **potentially vaccinated** if the positive vaccination status is based on recall alone and cannot be confirmed by registers, or is otherwise ambiguous.

A child aged < 9 years who has not been fully vaccinated (see above) during the previous influenza season will be considered as

- **vaccinated** with the influenza vaccine of interest if >14 days have elapsed since the second record of injectable vaccination or the first record of LAIV vaccination during the current season (see section *Vaccination status ascertainment*)
- partially vaccinated
  - during the first 14 days after the second record of injectable vaccination or the first record of LAIV vaccination during the current season
  - after the first record of injectable vaccination until >14 days have elapsed since the second record of vaccination during the current season
- **unvaccinated** until the first vaccination record during the season
- **potentially vaccinated** if the positive vaccination status is based on recall alone and cannot be confirmed by registers, or is otherwise ambiguous.

The *partially* and *potentially* vaccinated groups will be excluded from primary analysis; their significance will be assessed in sensitivity analyses.

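### Infants are eligible from 6 months at recruitment, but the youngest may be unable to meet the under-9 definition of vaccinated, so in the primary analysis they could serve only as comparators and could bias childhood VE in either direction

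*Combined protocol and SAP*

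**What the plan says.** **Entry.** Under Study population, patients are "aged 6 months and above, with no contraindication for influenza vaccination". The Exclusion criteria repeat the limit for both ILI and SARI patients and fix when it is judged: "Is less than 6 months of age at the time of recruitment".

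**Exposure.** Under Definition of vaccination status, a child under 9 who was not fully vaccinated in the previous season is:
- vaccinated "if >14 days have elapsed since the second record of injectable vaccination or the first record of LAIV vaccination during the current season";
- partially vaccinated "after the first record of injectable vaccination until >14 days have elapsed since the second record of vaccination during the current season", and also in the first 14 days after the second injectable dose or the first LAIV dose;
- unvaccinated "until the first vaccination record during the season".

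The partially and potentially "vaccinated groups will be excluded from primary analysis; their significance will be assessed in sensitivity analyses".

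**Age.** The Secondary objectives name the childhood stratum, "age group (6 months-14 years; 15-64 years; 65+ years", and say the groups will be defined further. Under Measure of effect, both crude VE and VE from a logistic model containing age are planned, but no form is given for the age term. Annex 1 records age in years and makes age in months obligatory under 1 year.

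The documents state no minimum age for vaccination, no interval between doses, and no influenza positivity by age.

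**The concern.** Entry depends on age at recruitment, while exposure depends on time elapsed since one or two doses. Nothing in the documents reconciles the two. If vaccination cannot start before 6 months, there is a short age window just above 6 months in which nobody can be classed as vaccinated. A dosed infant in that window is set aside as partially vaccinated. An undosed infant of the same age stays in the comparator.

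Such infants carry no information on the vaccinated-unvaccinated contrast at their age, yet they change the influenza positivity of the unvaccinated group. Annex 3 uses the same unvaccinated group for every brand, so in a crude analysis one distortion would reach each brand estimate, each type estimate and overall VE. The 6 months to 14 years stratum is most exposed. Hospital SARI studies would be affected more than primary care if young infants are a larger share there, but the documents give no age mix.

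**Working it through.** The plan gives no figure on this point, so there is none to reproduce. The check has two parts.

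**1. Earliest age at which an infant can be vaccinated**

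From the plan: more than 14 days, so at least 15, after the qualifying dose. Assumed: no vaccine before 6 months, and injectable doses 0, 21 or 28 days apart. An infant in this window cannot have been fully vaccinated last season, having then been younger than 6 months or unborn.

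Earliest age in months = 6 + (gap + 15)/30.44
- LAIV, or no gap: 6 + 15/30.44 = 6.5
- 21 days: 6 + 36/30.44 = 7.2
- 28 days: 6 + 43/30.44 = 7.4

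The window is therefore 15 to 43 days. Against the 14.5 years from 6 months to the 15th birthday, that is 15/(14.5 × 365.25) = 0.3% to 43/(14.5 × 365.25) = 0.8% of the age span.

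**2. Effect on childhood VE**

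True VE of 50% is the value the plan uses in Sample size considerations. The rest is assumed: 20% coverage and 40% positivity among the other unvaccinated children. Per 10,000 other children:
- 2,000 vaccinated: 500 positive, 1,500 negative
- 8,000 unvaccinated: 3,200 positive, 4,800 negative
- OR = (500 × 4,800)/(1,500 × 3,200) = 0.50

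Add infants, all unvaccinated, as 5% of the enlarged group: 10,000 × 0.05/0.95 = 526.3.
- Positivity 10% (52.6 positive, 473.7 negative): OR = (500 × 5,273.7)/(1,500 × 3,252.6) = 0.540, VE 46.0%
- Positivity 20% (105.3 and 421.1): OR = (500 × 5,221.1)/(1,500 × 3,305.3) = 0.527, VE 47.3%
- Positivity 40%: the positivity of the unvaccinated group is unchanged, VE 50.0%
- Positivity 50% (263.2 and 263.2): OR = (500 × 5,063.2)/(1,500 × 3,463.2) = 0.487, VE 51.3%

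The same calculation at other infant shares, with infant positivity from 10 to 20%:

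| Infant share | Crude VE |
|---|---|
| 1% | 49.2 to 49.5% |
| 3% | 47.6 to 48.4% |
| 5% | 46.0 to 47.3% |

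**Adjustment for age.** A weighted logistic model was fitted with other children spread over 0.75 to 14.5 years and the infants placed at 0.58 years (7.0 months).
- A linear age term gives 47.8 to 48.6% at a 3% share and 46.6 to 47.7% at 5%, little better than crude.
- Age categories (under 1, 1, 2 to 4, and 5 years or over) give about 49% at a 5% share.
- Giving these infants their own stratum returns 50.0%, because a stratum with no vaccinated subjects contributes nothing to a stratified odds ratio. Excluding them returns 50% for the same reason.

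**The case against.** The case against has real force on four counts.

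**Size.** The window is 0.3 to 0.8% of the childhood age span. At those shares, with 10 to 20% infant positivity, crude VE is 49.8% and 49.4 to 49.6% respectively. A 10% share, which would give 41.6 to 44.6%, needs a six-week age band to be over-represented about 12-fold (10/0.81). This stands: where infants are few, the effect is negligible.

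**Direction.** A reader might infer that these infants pull childhood VE down. The documents do not support that, since they give no positivity by age. In the set-up above, crude VE at a 5% share rises to 51.3% at 50% infant positivity and 52.5% at 60%.

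**Classification.** A reader might also infer that young infants can enter the study only as unvaccinated, or that dosed infants are miscounted as unvaccinated. Neither is so. A dosed infant is partially, or possibly potentially, vaccinated, is removed from the primary analysis only, and is kept for sensitivity analyses. The gap itself is also conditional, because the minimum vaccination age is an assumption and the 7.2 to 7.4 month figures need an assumed dose interval as well. The modelled position of 7.0 months lies inside the injectable window but outside the one that applies to every route.

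**Existing safeguards.** Age is in the minimum adjustment set and in the model, age groups are still to be refined, and sites may vary their exclusion criteria. A model in which low positivity ends abruptly is also unfavourable to age adjustment; a gradual change with age would be absorbed better. This weakens the point without disposing of it. The form of the age term is unspecified, crude VE is a planned estimate, and the main age variable is in years. Even one-year categories would mix infants inside the window with those beyond it. The listed sensitivity analyses are optional and do not name this one.

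**Conclusion.** The point holds as a conditional lack of overlap. If vaccine is not given before 6 months, infants below about 6.5 months at onset, or about 7.2 to 7.4 months on a two-dose injectable schedule with a 21 to 28 day gap, can be in the primary analysis only as comparators. Nothing in the documents corrects for this.

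Under the stated assumptions the crude loss is at most 0.8 points at a 1% infant share and 2.7 to 4.0 points at 5%. It is nil at equal positivity and becomes a gain if infants test positive more often. A linear age term barely helps, whereas categories that separate the first year recover most of the loss. The infant shares and positivities are illustrative. The point therefore supports an inexpensive clarification of the analysis set and the age term. It does not show that the planned estimates are biased in a known direction, and it gives no reason to change who is enrolled.

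**What to change.** Keep enrolment as it is and change the analysis plan:

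1. Limit the VE analysis (overall, by type and by brand) to children who, by age in months at symptom onset, were old enough to have met the definition of vaccinated. Derive the cut-off from each site's own earliest vaccination age and dose interval. A single fixed limit such as 8 months would overshoot the 6.5 to 7.4 months found above and drop infants who can be classed as vaccinated.
2. Specify age flexibly within 6 months to 14 years, using age in months under 1 year so that the term can change within the first year.
3. Report VE with and without the infants below the cut-off as a named sensitivity analysis. They can still be swabbed and described.

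**Cost.** No new variable is needed, since age in months is already obligatory under 1 year. Annex 1 should state that it refers to symptom onset, as it does for age in years, and how a cut-off falling within a month is rounded. A few weeks of age are lost, from subjects who carry no information on the contrast, and VE can no longer be described as applying from exactly 6 months.

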## Laboratory testing

Respiratory specimens will be collected from all eligible patients (ILI and/or SARI). We strongly encouraged the use of random sampling for primary care studies recruiting ILI (i.e. swabbing the first 3 ILI cases presenting to a GP on the second day of the week of practice) and all SARI cases (i.e. all SARI cases presenting at the Emergency department of an Hospital).

Laboratory confirmation should be done through one of the following laboratory tests: reverse transcription-polymerase chain reaction (recommended option), viral culture, and immunofluorescence or rapid influenza diagnostic tests. Each positive test result is to be classified by influenza type (A and B) and preferably also subtype/lineage (A/H1N1, A/H3N2, B/Victoria, and B/Yamagata).

- Each study site to describe the specimen collection (i.e. to include a description of the criteria and procedure for swabbing at the site level).
- > Each study site to describe the specimen storage & transport procedures
- Each study site to describe the laboratory tests used & the selection of specimens and the procedures for genetic and antigenic characterisation (see Annex 4 for an example of results presentation)
- Each study site to describe if the laboratory participates in QA/QC (Quality Assurance/Quality Control) schemes

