#### Representativeness of subjects included in the study

Study teams to describe the potential limitations in terms of representativeness of the subjects included

The study includes ILI and SARI cases. Health-seeking behaviour (referring to how individuals use health services: e.g. the decision to access healthcare, time from onset of illness to consultation, the type of healthcare provider consulted and the compliance to recommended treatment) may differ by country depending on the case management strategy (e.g. recommendation of seeing a GP first). In some cases, the management strategy will have an impact on the delay between onset of symptoms and hospitalisation. This, in turn, may have an impact on the time lag between onset and respiratory specimen collection, and may affect positivity rates between study sites. Beside the collection of dates of onset/admission/respiratory specimen collection, health-seeking behaviour and case-management strategy should be described for each study and it should be noted how it may affect the VE estimates.

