					1=Yes	
				Numeric	9999=No	
cough	Optional	Cough		(Categorical)	information	1
			Subjective evaluation of breathing			
			difficulty by patient or caregiver, or any			
			of the following: respiratory rate		0=No	
			≥25/min (adults) or SpO2 <90% (unless		1=Yes	
		Difficulty	chronic) or PaO2 <8 kPa or respiratory	Numeric	9999=No	
diffbreath	Optional	breathing	acidosis	(Categorical)	information	0
					0=No	
					1=Yes	
				Numeric	9999=No	
sorethroat	Optional	Sore throat		(Categorical)	information	1
		Deterioration of				
		general condition				
		(asthenia, loss of			0=No	
		weight, anorexia,			1=Yes	
		confusion or		Numeric	9999=No	
deterioration	Optional	dizziness)		(Categorical)	information	1
					0=No	
	Obligatory				1=Yes	
	(for	Influenza like		Numeric	9999=No	
ili	outpatient)	illness	Fulfilling the EU-ILI case definition	(Categorical)	information	1

n
n
n

(or alternatively

tutor, where

applicable)

Obligatory

consentkin

1

1

1

1

1

1=Yes

(Categorical) applicable

Numeric

9999=Not

	innovative medicines initiative
--	---------------------------------------

DRIVE 777363	3 – D7.1			Initiative		
comm	Optional	Whether communication with the patient OR consent from next of kin was possible.		Numeric (Categorical)	0=No 1=Yes 9999=No information	1
				(00008011001)		
inst	Obligatory	Institutionalized	Living in a residence or nursing home (any such institution where nurse present 24/7)	Numeric (Categorical)	0=No 1=Yes 9999=No information	0
		Did the patient				
		have a previous			0=No	
		lab-confirmed			1=Yes	
		influenza in this		Numeric	9999=No	
prevflu	Obligatory	season?		(Categorical)	information	0
	Obligate	Laboratory result:		Numeric	0=None 1=A 2=B 3=Other influenza not specified 4=Other virus 9999=No	
labvirusi	Ubligatory	virus type		(Categorical)	information	2

DRIVE 777363 – [	07.1		imi	innovative medicines initiative		
labsubtype1	Obligatory	Laboratory results: virus subtype		Numeric (Categorical)	0=None 1=A(H1N1)pdm09 2=A(H3N2) 3=B Yamagata 4=B Victoria 5=Other influenza 9=Other virus 9999=No information	3
labvirus2	Optional	Laboratory results: virus type (co-infection)		Numeric (Categorical)	0=None 1=A 2=B 3=Other influenza not specified 4=Other virus 9999=No information	2
labsubtype2	Optional	Laboratory results: virus subtype (co- infection)		Numeric (Categorical)	0=None 1=A(H1N1)pdm09 2=A(H3N2) 3=B Yamagata 4=B Victoria 5=Other influenza 9=Other virus 9999=No information	3

DRIVE ///363 -	D7.1	1		I	1 1
		Received		0=No	

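### The prior-influenza exclusion is worded in two ways that classify the same patient differently, and nothing limits one illness to one record within a setting

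*Combined protocol and SAP*

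**What the plan says.** The protocol's Exclusion criteria (under Case finding) state the rule three times.

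- The ILI list excludes a patient who "tested positive for any influenza virus in the current season before the onset of symptoms leading to the current primary care visit/hospitalisation".
- The SARI list excludes a patient who "tested positive for any influenza virus in the current season before the onset of symptoms leading to the current hospitalisation".
- The Note closing the section says "a patient can be selected several times as long as he/she does not have a previous laboratory confirmed influenza for the current season".

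The two bullets are anchored to onset of the current illness; the Note is not. Annex 1 (Minimum dataset) makes the field prevflu obligatory. It asks whether the patient had an earlier laboratory-confirmed influenza this season and is coded no, yes or no information. It has no onset anchor, and the legible dataset holds no date for the earlier test.

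Both lists also exclude a patient who "had a respiratory specimen taken ≥ 8 days after ILI onset". Two swabs in one illness, for example on days 2 and 5, can therefore both be valid. The legible text sets no minimum gap between selections and no requirement for a new onset. Case finding asks sites to report their exclusions only where these differ from the list.

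**The concern.** Take a patient swabbed positive by a GP on day 2 and admitted with SARI on day 5 of the same illness. The positive test came after onset, so the SARI bullet leaves the patient eligible as a hospital case. The Note, read literally, bars the patient, and prevflu would be coded yes. Because the list contains both rules, two sites can enrol different patients and each report full compliance.

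The Note's version also acts on one side only. It removes patients already found positive in this illness and keeps those found negative. In a test-negative design that is selection of cases by outcome, and it distorts the odds ratio if earlier confirmation is more common in one vaccination group.

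A second gap exists under either wording. A patient negative on day 2 and positive on day 5 has no earlier confirmed influenza at the second selection, so the same illness can supply a control and a case. Two negative swabs can supply two controls. Under the bullets, two positive swabs can supply two cases. With repeat visits in one setting, all of this happens inside a single analysis.

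**Working it through.** **Inputs.** True VE 50% (OR 0.50), 500 cases, 1:1 ratio and a two-sided 95% CI, from Sample size considerations and Annex 3. The shares of cases confirmed earlier in the same illness, and of illnesses entered twice, are assumptions; the documents give none.

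**The plan's own baseline.** Annex 3, equation (3): lower limit = 1 − exp[log(OR) + 1.96 × SE], with SE = √(1/a + 1/b + 1/c + 1/d). At 50% coverage the cells are a = 207.1, b = 292.9, c = 292.9, d = 207.1. SE = 0.1284 and the lower limit is 1 − 0.50 × exp(0.2517) = 35.7%. It is 31.2% at 20% coverage and 34.1% at 70%. The stated lower limit above 30% is reproduced.

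**One-sided exclusion under the Note.** Let qv and qu be the shares of vaccinated and unvaccinated hospital cases with a positive test earlier in the same illness. Cases become a(1 − qv) and c(1 − qu), and controls are unchanged, so

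observed OR = true OR × (1 − qv)/(1 − qu).

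| qv | qu | Observed OR | Observed VE |
|---|---|---|---|
| equal | equal | 0.50 | 50.0% |
| 4% | 2% | 0.50 × 0.96/0.98 = 0.490 | 51.0% |
| 10% | 5% | 0.50 × 0.90/0.95 = 0.474 | 52.6% |
| 20% | 10% | 0.50 × 0.80/0.90 = 0.444 | 55.6% |
| 5% | 10% | 0.50 × 0.95/0.90 = 0.528 | 47.2% |

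At a true VE of 20%, shares of 20% and 10% give 1 − 0.80 × 0.80/0.90 = 28.9%. Under the onset-anchored rule the factor is 1 and no such shift arises.

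**Repeat records within one setting (50% coverage).**

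- Cases duplicated at 10%, equally by vaccination: VE stays at 50%. SE² falls from 0.01649 to 0.01574, an SE ratio of 0.977, and the lower limit moves from 35.7% to 36.1%.
- Cases and controls both duplicated at 10%: the SE ratio is 1/√1.10 = 0.953 and the lower limit is 36.4%. The extra precision is not real.
- 5% of cases also entered as controls for the same illness: b = 292.9 + 0.05 × 207.1 = 303.2 and d = 207.1 + 0.05 × 292.9 = 221.8. OR = (207.1/292.9)/(303.2/221.8) = 0.517, so VE is 48.3%.

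**The case against.** The strongest reply is that the bullets are the exclusion criteria, that the Note only comments on repeat selection, and that its word for an earlier influenza naturally means an earlier illness. On that reading there is no conflict. It is a reasonable reading and probably the intended one, but nothing in the text says so. The obligatory data field repeats the unanchored form without a date, so the submitted data could not apply the bullets.

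The overlap may also be small. Laboratory testing encourages sampling in primary care, for example "swabbing the first 3 ILI cases presenting to a GP on the second day of the week of practice". To be lost, a case must have seen a GP, been sampled and tested positive before a hospital swab taken within 7 days of onset. This stands as a reason to expect figures near the top of the table. It is not a guarantee, because sampling is encouraged rather than required, and the Note covers any laboratory confirmation, not only study swabs.

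Adjustment for healthcare visits, a minimum-set confounder, would remove bias acting through them. However, Annex 1 makes gpvisit obligatory for GP studies only, so hospital studies need not supply it.

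A reader might infer that hospital VE is necessarily inflated, and most of all where patients see a GP first. The documents do not support this. Potential confounders lists healthcare seeking, and Addressing confounding & bias asks that it be measured and balanced, but neither says that vaccinated people consult more. Representativeness says that health-seeking behaviour "may differ by country depending on the case management strategy (e.g. recommendation of seeing a GP first", and goes on to swab delay and positivity, not to differences by vaccination status.

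A reader might also infer that counting an illness first as ILI and then as SARI is always double counting. The protocol defines separate primary care and hospital studies, and the generic SAP's example plot pools by setting. That overlap matters only if the settings are combined in one estimate.

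**Conclusion.** The inconsistency in wording stands: the same patient is eligible under the bullets and barred under the Note and prevflu read literally. The one-sided exclusion can bias hospital VE either way. Under the assumed shares, a true 50% becomes 51.0% to 55.6%, or 47.2% when the difference is reversed, and there is no bias when the shares are equal. With GP sampling, the smaller shifts are the more likely ones. They are modest beside a single site's interval (35.7% to 61.1% at 50% coverage), but pooling does not average them away if they run the same way across sites.

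The missing episode rule is a separate, smaller defect that holds under either wording. Its effects are slightly overstated precision and, where one illness gives both a control and a case, dilution of VE. The size of both effects depends on rates the documents do not give. The change is worth making because it is cheap and removes an outcome-dependent exclusion.

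**What to change.** 1. Reword the Note, and define prevflu as laboratory-confirmed influenza this season before the onset date recorded for this episode, so that both match the bullets.
2. Allow one record per patient per illness episode, identified by onset date, within a setting. Count it as a case if any study swab in that episode taken within the protocol's swab window is positive, and otherwise as one control.
3. If primary care and hospital data are combined in one estimate, apply the one-record rule across settings wherever records can be linked.

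The cost is a reworded Note, one field description and one counting rule. Sites must check their own study records for repeat swabs with the same onset date; no search of other providers' records for negative tests is needed. Patient identifier, onset date and swab date are already obligatory in Annex 1, so the pooled dataset can be checked too, provided the identifier stays with the patient across selections.
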